#### **Exclusion Criteria:**

- Acute subdural hematoma requiring emergency neurosurgical intervention
- Known vascular anomalies contraindicating embolization (e.g., high-risk leptomeningeal anastomoses)
- Missing or incomplete baseline clinical and radiological data
- Unavailability for prospective follow-up (e.g., no fixed address, no telephone contact)

## **5. Study Procedures and Timeline**

Treatment phase: MMAE is performed according to clinical routine (standard of care, no modifications).

#### **Study-specific additional assessments:**

##### **Clinical and quality-of-life assessments** (mRS, GOS-E, EQ-5D-5L, GCS, Markwalder score):

- Pre-interventionally (baseline)
- Day 30 (telephone interview)
- Day 90 (in-person or telephone, within the new cSDH outpatient clinic)
- Day 120 (telephone interview)

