## 2. Objectives

**Primary:** To identify clinical and radiological predictors of good functional outcome (mRS  $\leq 2$  at 90 days) after MMAE for cSDH.

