**Primary Endpoints:**

1. **Radiological response** – Change in hematoma volume/thickness at 3 months
2. **Clinical efficacy** – Re-intervention rate and functional outcome (mRS) at 90 days
3. **Clinical safety** – Occurrence of complications

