**Potential Confounders (Core Set):**

- Hematoma architecture
- Initial volume/thickness and localization
- Foramen spinosum diameter
- Anticoagulation / antiplatelet therapy
- Extent of embolization (vessel-branch level; embolic agent documented)

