## **6. Data Collection**

**Clinical:** Medical history, GCS, comorbidities, anticoagulation/antiplatelet therapy, symptom course

**Radiological:** Hematoma volume, architecture, laterality, localization, midline shift, MMA caliber, anatomical MMA variants, foramen spinosum diameter, prior burr-hole trepanation

**Procedural:** Embolic agent, BE-EMMA score, technical details, embolisation volume, degree of distal penetration, complications

**Follow-up:** mRS, GOS-E, EQ-5D-5L, GCS, Markwalder score at each time point; re-intervention, recurrence, mortality, symptom course

Documentation is performed in pseudonymized case report forms (CRF; currently Excel-based, with planned migration to REDCap).

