## 10. Statistics

Target sample size: 75–150 patients (exploratory).

Descriptive statistics with 95% confidence intervals; bivariate correlation analyses (Pearson or Spearman); logistic regression for predictor analysis. Missing data will be reported but not imputed.

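### Function before the hematoma is never recorded, so the predictor analysis of mRS ≤2 at 90 days cannot separate pre-existing disability from hematoma-related disability

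*Protocol*

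**What the plan says.** Section 2 of the protocol states the primary objective as "To identify clinical and radiological predictors of good functional outcome", defined as mRS ≤2 at 90 days. The clinical efficacy endpoint in the same section is "Re-intervention rate and functional outcome (mRS) at 90 days". Neither refers to the patient's function before the hematoma.

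Section 4 requires a confirmed chronic subdural hematoma and a baseline mRS of at most 3. It does not ask what caused the disability.

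Section 5 places the first functional assessment "Pre-interventionally (baseline"; the others are at days 30, 90 and 120.

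Section 6 lists the clinical items as "Medical history, GCS, comorbidities, anticoagulation/antiplatelet therapy, symptom course" and the functional scales as "mRS, GOS-E, EQ-5D-5L, GCS, Markwalder score at each time point". The list in Section 2 headed "Potential Confounders (Core Set" covers hematoma, anatomy, antithrombotic therapy and embolization. It contains neither pre-morbid function nor baseline mRS.

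Section 10 gives "Target sample size: 75–150 patients (exploratory" and names "logistic regression for predictor analysis".

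**The concern.** Two kinds of patient can enter at mRS 3. One lived at mRS 0–2 and was brought to 3 by the hematoma; this patient can return below the cut. The other lived at mRS 3 for unrelated reasons; this patient will rarely reach mRS ≤2, however well the hematoma resolves. The planned data give both the same baseline score.

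The main analysis relates baseline factors to the chance of mRS ≤2. A factor that is commoner among previously disabled patients will be associated with poor outcome even if it has no bearing on recovery. Antithrombotic therapy, a core-set item, is a plausible example. Section 9 names better patient selection as a benefit, so such an association could be read as a reason to treat or not to treat. The registry has a single arm, so there is no comparison group in which the same association would show up and give a warning.

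**Working it through.** **No stated figure to reproduce.** The target of 75–150 is labelled exploratory and has no event rate, effect size or power behind it. The gap is established by the text; the arithmetic only illustrates its possible size. Every share below is an assumption.

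**Step 1. How many patients could be affected.** Assume 20–40% enter at mRS 3 and a quarter to a half of these were at mRS 3 before the hematoma.
- Lower end: 0.20 × 0.25 = 5%, about 4 of 75 or 8 of 150.
- Upper end: 0.40 × 0.50 = 20%, 15 of 75 or 30 of 150.

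If none of them reaches mRS ≤2, the highest attainable good-outcome rate is 95% to 80%.

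**Step 2. Spurious association without adjustment.** Assume 12% of the cohort had pre-morbid mRS 3 and all are poor at 90 days; 15% of the other 88% are poor; a factor X is present in 60% of the first group and 32% of the second, and has no effect on recovery.
- Share of poor outcomes that come from the first group: 0.12 / (0.12 + 0.15 × 0.88) = 0.12 / 0.252 = 48%.
- With X: (0.072 + 0.15 × 0.2816) / 0.3536 = 0.323.
- Without X: (0.048 + 0.15 × 0.5984) / 0.6464 = 0.213.
- Odds ratio for poor outcome: (0.323/0.677) / (0.213/0.787) = 1.76.

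**Step 3. Does baseline mRS repair it?** Assume also that 30% of the cohort enters at mRS 3, so 18% is at mRS 3 because of the hematoma, and that 30% of those are poor. Among the remaining 70%, the poor rate is then (0.132 − 0.054) / 0.70 = 11.1%. Expected shares of the cohort:

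| Baseline mRS | X | All | Poor |
|---|---|---|---|
| 3 | yes | 0.1296 | 0.072 + 0.30 × 0.0576 = 0.0893 |
| 3 | no | 0.1704 | 0.048 + 0.30 × 0.1224 = 0.0847 |
| 0–2 | yes | 0.2240 | 0.0250 |
| 0–2 | no | 0.4760 | 0.0530 |

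- Within baseline mRS 3: risks 0.689 and 0.497, odds ratio 2.24 (1.72 with 6% and 2.63 with 18% pre-morbid mRS 3).
- Within baseline mRS 0–2: odds ratio 1.0.
- Logistic regression on these cells with X and baseline mRS (3 versus lower): odds ratio 1.52. On the log scale, 1 − ln 1.52 / ln 1.76 = about 0.26, so adjustment removes roughly a quarter of the distortion.

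**Step 4. Other assumptions, same direction.** Let 75% of patients without pre-morbid mRS 3 do well, and let pre-morbid mRS 3 be present in 10% versus 2%, 20% versus 5%, or 30% versus 10% of patients with and without the factor. The good-outcome rates are 0.675 vs 0.735, 0.600 vs 0.7125, and 0.525 vs 0.675. The odds ratios for good outcome are 0.75, 0.61 and 0.53.

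**Step 5. What a redefined outcome would do.** Suppose good outcome became mRS ≤2 or return to pre-morbid mRS. A patient with pre-morbid mRS 3 who enters at 3 meets this on the day of enrolment. If all of the 12% stay there, the poor risks in Step 2 become 0.15 × 0.2816 / 0.3536 = 0.119 and 0.15 × 0.5984 / 0.6464 = 0.139, an odds ratio of 0.84. The bias changes sign; it does not vanish.

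**Step 6. What recording the item would do.** In the Step 2 scenario X is unrelated to outcome within each level of pre-morbid mRS, so a model that contains the item returns an odds ratio of 1.0 for X, apart from recall error.

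**The case against.** The strongest case on the other side has four parts.

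*Prediction is not causation.* If the aim is only to forecast mRS ≤2, a marker of prior disability is a genuine predictor. This stands as far as it goes. But the protocol lists confounders and hopes to improve patient selection, so it intends more than a forecast. Even a pure forecast would gain from the item.

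*The size is assumed, and noise is larger.* This stands. In the Step 2 scenario with 150 patients, the standard error of the log odds ratio is √(1/17.1 + 1/35.9 + 1/20.7 + 1/76.3) = 0.38, so an odds ratio of 1.76 has a 95% interval of about 0.83–3.74; with 75 patients it is 0.61–5.11. The distortion would not stand out in this exploratory study. It would still be a bias, and without the item its size could never be checked.

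*History and comorbidities are collected.* They may hint at prior disability, but nothing in Section 6 makes them a graded measure of prior function.

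*A fixed mRS ≤2 is a legitimate endpoint.* It is, and nothing here requires changing it.

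A reader might also infer that the plan counts fully recovered patients as failures of MMAE and understates its success. The document does not support that. It speaks of predictors, not failures; it sets no benchmark for the good-outcome rate; and the efficacy endpoint names mRS without a cut. Given the entry cap, a patient with pre-morbid mRS 3 who enters at 3 has also not been moved to a worse grade by the hematoma.

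**Conclusion.** The gap is real and follows from the text alone. The cut is fixed at mRS ≤2, entry is open to mRS 3, the first score is taken with the hematoma present, and no listed item records earlier function. Because it concerns data collection, it cannot be left to an analysis plan.

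Its size is unknown. Under the assumed inputs, 5–20% of the cohort would be affected, and an irrelevant factor could show an odds ratio for poor outcome of 1.76 before and 1.52 after adjustment for baseline mRS. These figures show a mechanism and are not estimates for this cohort.

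Two stronger readings should be avoided. One is that adjusting for baseline mRS is useless: it helps in part. The other is that the outcome must be redefined as return to prior function: that would count some patients as good from enrolment and turn the bias round. This is a worthwhile, inexpensive improvement, not a flaw that invalidates the registry.

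**What to change.** - Add *pre-morbid mRS (before onset of cSDH symptoms)* to the baseline assessment in Section 5 and to the clinical items in Section 6.
- Add it to the confounder core set in Section 2, and include it together with baseline mRS as a covariate in the logistic regression of Section 10.
- Keep mRS ≤2 at 90 days as the definition of good outcome. Use mRS ≤2 or return to pre-morbid mRS at most as a sensitivity analysis, with a note that patients entering at a pre-morbid mRS of 3 already meet it.

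The cost is one question at an interview already planned, one field in a case report form that is due to migrate to REDCap anyway, and one extra model term. The item relies on recall by the patient or a relative, so some misclassification and residual confounding will remain. If nearly all patients with pre-morbid mRS 3 have a poor outcome, the coefficient of the new term may not be estimable by ordinary maximum likelihood; a penalized fit (Firth) deals with this.

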##### **Imaging follow-up** (cranial CT):

- Within 7 days post-intervention
- At 3 months post-intervention (within the new cSDH outpatient clinic)

**Note:** Compared to the currently heterogeneous clinical routine at the Charité, these assessments may result in one additional CT for some patients. The chosen time points are fully consistent with the recommendations of the international ARISE-I consensus, which endorses early follow-up imaging and a 3-month control CT. The use of ionizing radiation in this study has been approved in accordance with the German Radiation Protection Act (Strahlenschutzgesetz) and the applicable regulatory requirements of the Federal Office for Radiation Protection (Bundesamt für Strahlenschutz, BfS).

## **6. Data Collection**

**Clinical:** Medical history, GCS, comorbidities, anticoagulation/antiplatelet therapy, symptom course

**Radiological:** Hematoma volume, architecture, laterality, localization, midline shift, MMA caliber, anatomical MMA variants, foramen spinosum diameter, prior burr-hole trepanation

**Procedural:** Embolic agent, BE-EMMA score, technical details, embolisation volume, degree of distal penetration, complications

**Follow-up:** mRS, GOS-E, EQ-5D-5L, GCS, Markwalder score at each time point; re-intervention, recurrence, mortality, symptom course

Documentation is performed in pseudonymized case report forms (CRF; currently Excel-based, with planned migration to REDCap).

## **7. Data Protection**

- Pseudonymization via study-specific ID
- Separate, encrypted assignment list

- Storage exclusively on Charité servers (clinical data: 10 years; CT data: 30 years)
- Access restricted to authorized study personnel only
- Data processing in compliance with DSGVO and BlnDSG

## 8. Risks and Burden

- Radiation exposure from up to two additional native low-dose CTs (7 days, 3 months) – within diagnostically acceptable dose ranges (ALARA principle)
- Minimal time investment for structured follow-up interviews (telephone or in-person, approximately 10–15 minutes each at days 30, 90, and 120)
- No additional medical interventions or modifications to clinical care
- No further medical risks

## 9. Benefits

### Individual Benefits:

- Close structured follow-up
- Early detection of complications
- Objectified assessment of treatment course

### Benefits for Future Patients:

- Validation of a clinically applicable and standardized follow-up protocol
- Improved patient selection and treatment planning in the future
- Contribution to establishing MMAE as a safe and effective therapy in Germany

## 10. Statistics

Target sample size: 75–150 patients (exploratory).

Descriptive statistics with 95% confidence intervals; bivariate correlation analyses (Pearson or Spearman); logistic regression for predictor analysis. Missing data will be reported but not imputed.

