## 4. Eligibility Criteria

**Inclusion Criteria:**

- CT- or MRI-confirmed chronic subdural hematoma (cSDH)
- Planned or completed MMAE (primary therapy or adjunct to surgical evacuation)
- Age  $\geq 18$  years
- Written informed consent including agreement to extended follow-up (CT and clinical assessments)

- mRS  $\leq 3$  at baseline

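### The no-imputation rule commits the Day-90 mRS analysis to complete cases, although Day-30 and Day-120 scores that could inform a missing value are already collected

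*Protocol*

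**What the plan says.** The primary objective (Section 2) is "To identify clinical and radiological predictors of good functional outcome", defined as mRS 2 or lower at 90 days. Functional outcome at 90 days also appears in Section 2 among the primary endpoints, under clinical efficacy. Section 10 plans descriptive statistics with 95% confidence intervals and "logistic regression for predictor analysis", for an exploratory target of 75–150 patients. On missing values it says only: "Missing data will be reported but not imputed".

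Section 5 schedules mRS and GOS-E at baseline and at Days 30, 90 and 120; the last entry begins "Day 120 (telephone interview". Day 90 may be done in person or by telephone. Section 6 lists the same scales for every follow-up time point, together with re-intervention and mortality.

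Two exclusion criteria in Section 4 bear on completeness: "Missing or incomplete baseline clinical and radiological data" and "Unavailability for prospective follow-up (e.g., no fixed address, no telephone contact". Inclusion requires "Written informed consent including agreement to extended follow-up (CT and clinical assessments". The protocol gives no expected loss to follow-up, no expected good-outcome rate and no assumption about why data would be missing.

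**The concern.** An ordinary logistic model without imputation uses only patients with the Day-90 mRS and every covariate in the model. The same restriction applies to the good-outcome proportion and its confidence interval. A patient missed at Day 90 but reached at Day 30 or Day 120 contributes nothing to either, although a score taken 60 days earlier or 30 days later says a good deal about the missing one.

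This is not a detail left open for a statistical analysis plan. The protocol states the rule positively, so a later plan that used multiple imputation would contradict it.

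Three things are at stake: the good-outcome rate, if those lost differ from those kept; the predictor odds ratios, under a narrower condition; and the number of poor outcomes, which limits how many predictors a logistic model can support in a study this small.

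**Working it through.** The sample size is given without inputs, so the plan has no figure to reproduce. The sample sizes 75 and 150 come from Sections 3 and 10. **Every rate below is an assumption.**

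**1. Good-outcome rate.** Let *m* be the fraction without a Day-90 mRS, 80% the good-outcome rate among those observed, and *q* the rate among the missing. The true rate is (1 − *m*) × 0.80 + *m* × *q*, so complete cases overstate it by *m* × (0.80 − *q*).

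| *m* | *q* | True rate | Overstatement |
|---|---|---|---|
| 5% | 60% / 40% | 79% / 78% | 1 / 2 points |
| 10% | 60% | 0.72 + 0.06 = 78% | 2 points |
| 15% | 50% | 0.68 + 0.075 = 75.5% | 4.5 points |
| 20% | 40% | 0.64 + 0.08 = 72% | 8 points |
| 10–20% | 80% | 80% | 0 |
| 10–20% | 90% | 81–82% | −1 to −2 points |

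The sign can also be checked from the true rate. With true rate *p*, and missing fractions *g* among good and *b* among poor outcomes, the observed rate is *p*(1 − *g*) / [*p*(1 − *g*) + (1 − *p*)(1 − *b*)]. At *p* = 70%:

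- *g* = 5%, *b* = 15%: 0.665 / 0.920 = 72.3% (+2.3 points)
- *g* = 5%, *b* = 30%: 0.665 / 0.875 = 76.0% (+6.0)
- *g* = *b* = 10%: 70.0% (0)
- *g* = 15%, *b* = 5%: 0.595 / 0.880 = 67.6% (−2.4)

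For scale, with 15% missing and 80% good observed, the 95% half-width is 1.96 × √(0.16 / 63.75) = 9.8 points at n = 75 and 1.96 × √(0.16 / 127.5) = 6.9 points at n = 150. A bias of 4.5 points is thus about half to two-thirds of the half-width, and the interval does not reflect it.

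**2. Predictor odds ratio.** Take a binary predictor with good outcome in 80% without it and 60% with it. The true odds ratio is (0.6 × 0.2) / (0.4 × 0.8) = 0.375. Complete cases multiply this by *r*(good, with) × *r*(poor, without) / [*r*(poor, with) × *r*(good, without)], where *r* is the fraction retained.

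- Loss by outcome only (30% of poor, 5% of good): the factor is 1 and the odds ratio stays 0.375.
- Loss by predictor only (5% against 30%): the factor is 1 and it stays 0.375.
- 30% lost among poor outcomes with the predictor, 5% elsewhere: 0.375 × 0.95 / 0.70 = 0.509.
- 30% lost among poor outcomes without the predictor, 5% elsewhere: 0.375 × 0.70 / 0.95 = 0.276.

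Bias therefore needs a retention pattern that does not split into an outcome part and a predictor part, and it can go either way.

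**3. Lost information.** Complete cases fall from 75 to 67.5 at 10% missing and to 60 at 20%; from 150 they fall to 135 and 120. At n = 75, 15% missing and 80% good observed, 63.75 patients remain, with 63.75 × 0.20 = 12.75 poor outcomes. Among the 11.25 lost, the poor outcomes number:

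- 11.25 × 0.20 = 2.25 if the lost resemble the kept, which is 2.25 / 15 = 15% of all poor outcomes
- 11.25 × 0.50 = 5.6 if half the lost did badly, which is 5.6 / 18.4 = about 31%

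**4. What bounds would show.** With 80% good observed, counting all missing as poor and then all as good gives 72–82% at 10% missing, 68–83% at 15% and 64–84% at 20%.

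**The case against.** The strongest reply is that nothing in the protocol shows harm. No loss rate or pattern of loss is given. Day 90 can be done by telephone, patients without telephone contact are excluded, and consent to extended follow-up is required, so loss may be small. The study is exploratory, and its primary objective concerns odds ratios, which outcome-driven loss alone leaves intact. Multiple imputation helps only as far as the variables used explain why values are missing. All of this stands. It limits the size of the point, but it is no reason to rule imputation out in advance.

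Several stronger readings are tempting but not supported:

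- **That the analysis favours good outcomes.** This is plausible if patients doing badly are harder to reach, but the documents do not show it, and the sign reverses if patients doing well stop attending.
- **That the baseline exclusion and the no-imputation rule compound into a double selection bias.** The exclusion concerns baseline data and by itself mainly limits whom the results apply to. It also makes baseline covariates more complete. Because enrolment after a completed embolization is allowed, it could be applied once the early course is known, but the protocol does not say that it is.
- **That patients unable to complete the EQ-5D-5L are excluded.** The criterion names clinical and radiological data. Section 5 distinguishes clinical from quality-of-life assessments, and the clinical list in Section 6 omits the EQ-5D-5L.
- **That deaths fall out of the mRS analysis.** Listing mortality separately does not remove deaths from the mRS. Scoring a known death is not imputation, so Section 10 does not forbid it.
- **That the Day-30 and Day-120 scores are discarded.** They are collected and can be reported; they are only barred from informing a missing Day-90 value.

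**Conclusion.** The point holds as a recommended change. Section 10 fixes a complete-case analysis of the Day-90 mRS when a better use of data already scheduled is available.

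For the good-outcome rate, the illustrative overstatement is 2–8 points (4.5 in the middle case), resting wholly on assumed values of 80% good observed, 10–20% missing and 40–60% good among the missing. It is 1–2 points at 5% missing, zero if the missing resemble the observed, and negative if they do better. For the predictor odds ratios, bias arises only under joint dependence on outcome and predictor, with no predictable direction. Failing that, the cost is precision: in the middle case at n = 75, about 13 poor outcomes remain out of about 18. Imputation recovers part of that loss, to the extent that the other visits predict Day 90.

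**What to change.** Replace the missing-data sentence in Section 10 with a rule along these lines:

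- Deaths by Day 90 count as mRS 6. They are known outcomes and are not imputed.
- Missing Day-90 mRS and missing model covariates are multiply imputed under a stated missing-at-random assumption, using baseline variables, Day-30 and Day-120 mRS and GOS-E, and re-intervention. The follow-up scores enter the imputation model only and are not candidate predictors.
- The complete-case analysis and best/worst-case bounds for the good-outcome rate are reported alongside. The bounds cover the case where missing-at-random fails.
- The amount of missing data is still reported, and so is the number of screened patients excluded for incomplete baseline data, since counts among enrolled patients will not show them.

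The cost is modest extra analysis work, an assumption that must be stated and cannot be fully tested, and a count from the screening records. No new follow-up data and no change to eligibility are needed.

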## 11. Ethics and Legal Framework

- Conducted in accordance with the Declaration of Helsinki, GCP, and DSGVO
- Participation is voluntary and may be withdrawn at any time without consequences for clinical care
- Positive ethics committee vote required prior to study initiation
- Radiation protection approval granted by the Federal Office for Radiation Protection (Bundesamt für Strahlenschutz, BfS) in accordance with the German Radiation Protection Act (Strahlenschutzgesetz)
